11.2 Study Endpoints

The principal endpoints are the proportion of patients who are free of serious treatment related toxicity as discussed below and the proportion of patients who are free of breast cancer in the treated breast (IBTR). Secondary endpoints are the proportion of patients who are free of breast cancer in the regional lymph nodes (ipsilateral axilla, infraclavicular, supraclavicular, and internal mammary groups), free from distant disease, and proportion surviving. Additional secondary endpoints are quality of life as measured by the EORTC QLQ-C3 and QLQ-BR23, cosmesis as measured quantitatively by the BRA and pBRA, cosmesis as measured qualitatively by the Aronson modified Harris scale, the presence or absence of complications, the occurrence of mastectomy after completion of initial breast-conserving treatment and the frequency of any CTCAE v4.0 grade 3-4 toxicities.

11.3 Study Design and Analysis Plan

This is a single arm, non-randomized phase I/II study of 50 patients with stage 0 (tumor size $\leq 2\text{cm}$) or I breast cancer. The primary study goal is to quantify the tolerance of HG-PBI by estimating the rate of acute and late treatment-related grade 3 or higher toxicity (per CTCAE, v.4.0) or any other grade 4 or 5 toxicity attributed to the therapy. Toxicities of concern include breast pain, delayed wound healing, persistent seroma fluid accumulation, breast fibrosis and fat necrosis in the treated breast. Rare toxicities include radiation pneumonitis and pericarditis. These are expected to occur in approximately 5-8% of patients with a maximum allowable proportion with grade 3-5 toxicities of 12%. A sequential probability ratio stopping rule will be used to monitor the toxicity rate during the trial. For example, the study will be suspended for review of toxicity if 4 cases of grade 3-5 toxicity are seen among the first 14 patients, or 5 among the first 26 patients. The full criteria for monitoring are given in the table below. All toxicities and other serious adverse events will be reported to the Clinical Trials Office and to QASM as described.

The study will be suspended for review if:	
this number of patients are	before this number of patients

observed with grade 3-5 toxicity:	have completed the trial:
4	14
5	26
6	38
7	50

Patients will be followed for 5 years. The primary goals of the study involve tolerance to treatment; the proportion of patients who are breast cancer free 5 years after treatment will be calculated with a 95% confidence interval. Cosmetic outcome will be assessed qualitatively by patients and physicians over the years after treatment. The two sets of scores will be plotted using histograms showing the proportion rating the outcome excellent, good, fair and poor. Kappa statistics with 95% confidence intervals will be calculated to assess the agreement between patient and physician scores before treatment, at 4-6 months at 1 year, and at subsequent visits. The pBRA will be used to assess cosmesis quantitatively. This instrument includes a formula expressing the extent of displacement of the treated breast relative to the contralateral breast and other anatomical features. pBRA scores will be plotted at the assessment points and presented graphically. Quality of life will be assessed using the 30 items of the EORTC QLQ-C30 and 23 items of the QLQ-B23 and the Visual Analog Scale for Pain. The QLQ-C30 includes 6 general questions and 24 questions in 9 subscales measuring physical, role, emotional, cognitive and social function, as well as global health status, nausea/ vomiting, pain and fatigue. The QLQ-B23 provides 23 questions in 8 breast cancer specific subscales, 4 measuring symptoms and 4 measuring function. Each of the subscales will be tabulated and presented graphically over the assessment times. Mixed repeated measures models will be generated to describe the nature of change in quality of life over time. Complications will be tabulated and frequencies presented graphically. The rate of mastectomy within five years of treatment will be calculated with a 95% confidence interval.

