9.2 Reporting to the Human Research Protection Office (HRPO) at Washington University

The PI is required to promptly notify the IRB of the following events:

- Any unanticipated problems involving risks to participants or others which occur at WU, any BJH or SLCH institution, or that impacts participants or the conduct of the study.
- Noncompliance with federal regulations or the requirements or determinations of the IRB.
- Receipt of new information that may impact the willingness of participants to participate or continue participation in the research study.

These events must be reported to the IRB within **10 working days** of the occurrence of the event or notification to the PI of the event. The death of a research participant that qualifies as a reportable event should be reported within **1 working day** of the occurrence of the event or notification to the PI of the event.

9.3 Reporting to the Quality Assurance and Safety Monitoring Committee (QASMC) at Washington University

The PI is required to notify the QASMC of any unanticipated problem occurring at WU or any BJH or SLCH institution that has been reported to and acknowledged by HRPO as reportable. (Unanticipated problems reported to HRPO and withdrawn during the review process need not be reported to QASMC.)

QASMC must be notified within 10 days of receipt of IRB acknowledgment via email to a QASMC auditor.

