10.0 DATA AND SAFETY MONITORING

In compliance with the Washington University Institutional Data and Safety Monitoring Plan, the Principal Investigator will provide a Data and Safety Monitoring (DSM) report to the Washington University Quality Assurance and Safety Monitoring Committee (QASMC) semi-annually beginning six months after accrual has opened (if at least five patients have been enrolled) or one year after accrual has opened (if fewer than five patients have been enrolled at the six-month mark).

The Principal Investigator will review all patient data at least every six months, and provide a semi-annual report to the QASMC. This report will include:

- HRPO protocol number, protocol title, Principal Investigator name, data coordinator name, regulatory coordinator name, and statistician
- Date of initial HRPO approval, date of most recent consent HRPO approval/revision, date of HRPO expiration, date of most recent QA audit, study status, and phase of study
- History of study including summary of substantive amendments; summary of accrual suspensions including start/stop dates and reason; and summary of protocol exceptions, error, or breach of confidentiality including start/stop dates and reason
- Study-wide target accrual and study-wide actual accrual
- Protocol activation date
- Average rate of accrual observed in year 1, year 2, and subsequent years
- Expected accrual end date
- Objectives of protocol with supporting data and list the number of participants who have met each objective
- Measures of efficacy
- Early stopping rules with supporting data and list the number of participants who have met the early stopping rules
- Summary of toxicities
- Abstract submissions/publications
- Summary of any recent literature that may affect the safety or ethics of the study

The study principal investigator and Research Patient Coordinator will monitor for serious toxicities on an ongoing basis. Once the principal investigator or Research Patient Coordinator becomes aware of an adverse event, the AE will be reported to the HRPO and QASMC according to institutional guidelines.

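### The only toxicity suspension rule in the protocol pools grades 3-5 and first triggers at 4 patients, so one to three deaths attributed to HG-PBI, with no other grade 3-5 toxicity, would not require a pause

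*Combined protocol and SAP*

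**What the plan says.** Section 11.3 expects grade 3-5 toxicity in about 5-8% of patients and allows at most 12%. It monitors the rate with a sequential probability ratio rule and gives the first row in words: "the study will be suspended for review of toxicity if 4 cases of grade 3-5 toxicity are seen among the first 14 patients". The remaining rows are 5 patients by 26, 6 by 38 and 7 by 50. The section presents this as complete: "The full criteria for monitoring are given in the table below". No row or sentence treats grade 4, grade 5 or death separately.

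The other provisions that touch on a death are these:

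- **Section 9.2.** "The death of a research participant that qualifies as a reportable event should be reported within" 1 working day, to the IRB.
- **Section 9.3.** For unanticipated problems that HRPO has acknowledged as reportable, "QASMC must be notified within 10 days of receipt of IRB acknowledgment".
- **Section 9.4.** Reportable events are tracked for 30 days after treatment.
- **Section 10.0.** Serious toxicities are watched continuously, and once one is known "the AE will be reported to the HRPO and QASMC according to institutional guidelines". The semi-annual report must cover "Early stopping rules with supporting data and list the number of participants who have met the early stopping rules". The section opens "In compliance with the Washington University Institutional Data and Safety Monitoring Plan"; that plan is not part of the document.
- **Section 11.3.** "All toxicities and other serious adverse events will be reported to the Clinical Trials Office and to QASM as described".
- **Section 5.4.** The cancer center may close the study.
- **Section 11.5.** A repeated check covers recurrence in the treated breast, not toxicity.

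**The concern.** A rule on a pooled count gives a fatal event the same weight as a grade 3 local effect. That is reasonable when the question is whether the overall rate has drifted above 12%. It does not answer whether further patients should be treated before an attributed death has been examined.

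These are patients with low-risk stage 0 or I disease, and Section 1.1 says the center already offers them other APBI techniques or whole breast irradiation. One attributed death could change the balance of risk and benefit well before the count reaches four. Under the text as written, the death is handled through reporting, and treatment of new patients may continue meanwhile. Each patient receives a single fraction, so a pause protects only those not yet treated. What is at stake is confined to the period while accrual is open.

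**Working it through.** **Inputs.** From 11.3: trigger counts 4, 5, 6 and 7 at 14, 26, 38 and 50 patients; expected rate 5-8%; maximum 12%. From 11.6: 55 patients to be accrued, at about 25 a year. The documents give no fatal rate, no distribution of event times, and no error rates for the sequential rule. Those are assumptions where used below.

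**1. Reproducing the table.** The upper Wald boundary is r = h + s·n, with d = ln[p1(1−p0)/(p0(1−p1))], s = ln[(1−p0)/(1−p1)]/d and h = ln[(1−β)/α]/d. Take p0 = 0.05 and p1 = 0.12 from the plan, and assume α = 0.05 and β = 0.20.

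- d = 0.952
- s = 0.0765/0.952 = 0.0804
- h = ln(16)/0.952 = 2.912

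Solving n = (r − h)/s for r = 4, 5, 6 and 7 gives 13.5, 26.0, 38.4 and 50.8, against the stated 14, 26, 38 and 50. The table is what a test of 5% against 12% would produce.

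**2. Deaths alone.** The smallest count in any row is 4. One, two or three attributed deaths with no other grade 3-5 toxicity are below every row, whatever their timing. Three deaths among the first 14 patients would be 3/14 = 21.4%, and still no row is met. This step needs no assumption.

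**3. One death with background toxicity, first 14 patients treated.** With one attributed death, no suspension by patient 14 needs at most 2 events among the other 13: P(Bin(13, p) ≤ 2).

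- p = 0.05: 0.5133 + 0.3512 + 0.1109 = 0.975
- p = 0.08: 0.3383 + 0.3824 + 0.1995 = 0.920

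For comparison, with no death and all 14 patients at rate p, P(Bin(14, p) ≤ 3) = 0.996 and 0.979. The death moves the chance of no required pause only from 99.6% to 97.5%, or from 97.9% to 92.0%.

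**4. One death over all 50 patients treated.** Exact recursion through the four rows, with the death equally likely at each position, gives suspension by patient 50 with probability 5.6% (p = 0.05) to 24.3% (p = 0.08). Without the death the figures are 2.1% and 13.5%.

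**5. Is a pause required elsewhere?** Sections 9.2, 9.3, 10.0 and 11.3 say who is told. Section 5.4 permits closure without requiring it. Section 11.5 concerns recurrence. The stopping rules to be listed in the 10.0 report are, for toxicity, the same table. No section supplies the missing trigger.

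**6. Cost of a grade 5 trigger.** At an assumed fatal rate q, the chance of any attributed death in 55 patients is 1 − (1 − q)^55. This is an upper bound on the chance of an extra pause, because deaths after accrual closes pause nothing.

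| q | Upper bound | Death times uniform over 5 years |
|---|---|---|
| 0.1% | 5% | 1.2% |
| 0.5% | 24% | 5.9% |
| 1% | 42% | 11% |

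The last column assumes even accrual over 55/25 = 2.2 years. The share of deaths falling within accrual is then the mean remaining accrual time over 5 years, 1.1/5 = 0.22, and the chance of a pause is 1 − (1 − 0.22q)^55.

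**The case against.** The rule's declared job is to monitor a rate, and it does that. Nothing in the plan promises a reaction to a single event, and nothing is miscalculated. The hazard is also remote. Treatment is one fraction to part of the breast, Section 5.2.5.2 limits ipsilateral lung maximum dose to 7 Gy and heart V5 to 2%, the toxicities of concern are mainly local, and pneumonitis and pericarditis are listed as rare. All of this stands, and it keeps the point at the level of an optional improvement.

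A reader might infer that patients would go unprotected after an attributed death. The documents do not support that. An unexpected, related death would probably meet the definition of an unanticipated problem in 9.1.5 and so reach the IRB. The investigator, the IRB, QASMC or the cancer center could then pause the study, and the 10.0 report already provides for recording accrual suspensions. The institutional plan cited in 10.0 may itself require a pause. The gap shown is between a discretionary pause and an automatic one, within this protocol's own text.

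A reader might also infer the reverse, that prompt reporting at least is certain. That too goes beyond the text. The 1-day duty applies to a death that qualifies as reportable, and 9.4 tracks reportable events for only 30 days, although the toxicity endpoint includes late effects. The statements in 10.0 and 11.3 carry no time limit of their own.

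Finally, the table counts patients who have completed the trial, which could mean 5-year follow-up, whereas the sentence above it speaks of the first patients. Under the follow-up reading, the chance of suspension depends almost wholly on assumed event times, so no single figure is defensible. Step 2 of the working holds under either reading; steps 3 and 4 use the count of patients treated.

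**Conclusion.** The point holds as a statement about this protocol's text. For one to three attributed deaths with no other grade 3-5 toxicity, it follows from the printed table alone. With one attributed death among the first 14 patients treated and the plan's own 5-8% rate in the others, no suspension is required by patient 14 with probability 98% to 92%. That figure assumes independent events and indexing by patients treated.

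The table is sound for the overall toxicity rate, and the finding is no reason to redraw it. An attributed death is unlikely, and an automatic pause can help only while patients remain to be treated. In the illustration where death times are uniform over 5 years, only about 22% of such deaths fall in that window. This is a low-priority improvement that is worth making because it costs so little.

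**What to change.** Leave the four rows as they are and add one sentence to 11.3, for example: while accrual is open, accrual and treatment of further patients are also suspended for review by the principal investigator and QASMC after any grade 5 toxicity attributed to HG-PBI, whatever the time since treatment. List this trigger with the early stopping rules in the 10.0 report. Attribution can follow the endpoint wording already in 2.1 and 11.3, and the reviewers can decide on restarting, as they must for the existing rows. If the institutional plan already requires such a pause, a cross-reference in 11.3 is enough.

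The table, the sample size and the committees do not change, though QASMC gains an occasional review outside its semi-annual cycle. The downside is an occasional extra pause: at most 5%, 24% or 42% at assumed fatal rates of 0.1%, 0.5% or 1% in 55 patients, and lower when deaths fall after accrual closes.

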11.4 Sample Size and Study Power

Although the primary goals of this study include tolerance to treatment, the sample size for this study is based on the proportion of patients who remain free from an ipsilateral breast cancer recurrence (IBTR) 5 years after treatment which will be compared with the current expected value in the medical literature. Fyles reported that the five-year IBTR in a large population of women ≥ 50 yr with pT1N0 estrogen receptor positive breast cancers treated with partial mastectomy and tamoxifen but no radiation therapy was 5.9%[39]. HG-PBI will be considered worthy of further investigation if 1) the treatment-related toxicity rate as described above is less than 12% and 2) the five-year IBTR is not significantly greater than 10% higher than that observed in the Fyles study. Binomial proportion power analysis, assuming an alpha-level of 0.05, determined that we will obtain approximately 70% power to detect a proportion significantly larger than 15.9% given the true five-year IBTR is the same as that observed in the Fyles study. If 50 patients complete the trial and more than 3 recurrences are observed in the first five years, then the observed rate will be significantly larger than the acceptable proportion. Consequently, if 3 or fewer recurrences are observed among 50 patients and the tolerance parameters are met, the study will conclude that there is preliminary evidence that HG-PBI as performed in this trial is worthy of further study.

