11.0 STATISTICAL CONSIDERATIONS

11.1 Specific Aims

11.1.1 Specific Aim 1

We will quantify the tolerance of HG-PBI by estimating the rate of acute and late treatment-related grade 3 or higher toxicity (per CTCAE, v.4.0) or any other grade 4 or 5 toxicity attributed to the therapy. Toxicities of concern include breast pain, delayed wound healing, persistent seroma fluid accumulation, breast fibrosis and fat necrosis in the treated breast.

Rare toxicities include radiation pneumonitis and pericarditis. *Hypothesis:* Morbidity occurs in approximately 5-8% of patients with a maximum allowable proportion with grade 3-5 toxicities of 12%. A sequential probability ratio stopping rule will be used to monitor the toxicity rate during the trial.

11.1.2 Specific Aim 2

We will estimate the ipsilateral breast tumor recurrence rate at 5 years after HG-PBI as the sole radiation therapy technique following partial mastectomy. *Hypothesis:* The IBTR will be less than 15.9% with 95% confidence resulting in a treatment strategy worthy of further investigation in a larger clinical trial.

11.1.3 Specific Aim 3

We will estimate the change in breast cosmesis over time using the validated, quantitative parameter pBRA. *Hypothesis:* The pBRA will not significantly change over time. We have previously demonstrated this in the setting of multicatheter APBI.[20]

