11.6 Accrual

It is estimated that less than 10% of the patients treated in this study will be lost to follow up. Therefore, because the accrual goal is 50 evaluable patients (at 5 years post-treatment), target accrual is 55 patients to account for the 10% anticipated drop-out. It is estimated that patient accrual will take two to three years.

The investigators are well aware that several prior clinical trials that involved breast cancer at the Washington University Medical Center and the Siteman Cancer Center suffered from poor accrual. We believe that this trial will have excellent patient accrual. The primary source of patients who may be eligible for this study is via the breast surgeons of the Section of Endocrine and Oncologic Surgery here at Washington University. The chief breast surgeon is a collaborator in this study and is very supportive. The fact that a large fraction of patients with a common cancer disease are eligible for this study should lend further reassurance that this study ought to enjoy excellent patient accrual. The following series of conservative estimates provide an approximation of patient accrual: in 2012 more than four hundred patients with breast cancer were seen by physicians in the Department of Radiation Oncology. A conservative estimate is that 20% of these patients had an early stage breast cancer that would be eligible for this study. A further conservative estimate is that a third of these patients will consent to participate in this study. This yields an estimated accrual of just over 25 patients per year.

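### Section 11.4 states the IBTR test in the wrong direction, and its second success criterion conflicts with its own rule of 3 or fewer recurrences in 50

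*Combined protocol and SAP*

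**What the plan says.** Section 11.4 takes a five-year IBTR of 5.9% from a cited study of surgery and tamoxifen without radiotherapy and adds 10 percentage points to reach a limit of 15.9%. It then makes four statements about the IBTR decision.

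- The second condition for further investigation is that "the five-year IBTR is not significantly greater than 10% higher than that observed in the" cited study.
- On power: "Binomial proportion power analysis, assuming an alpha-level of 0.05, determined that we will obtain approximately 70% power". The sentence goes on to define this as "power to detect a proportion significantly larger than 15.9% given the true five-year IBTR is the same as that observed" in that study. It does not say whether alpha is one-sided or two-sided.
- On failure: with more than 3 recurrences among 50 completers, "then the observed rate will be significantly larger than the acceptable proportion".
- On success: HG-PBI merits further study "if 3 or fewer recurrences are observed among 50 patients and the tolerance parameters are met".

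Two other places bear on the same decision. Aim 2 (Section 11.1.2) gives the hypothesis as "The IBTR will be less than 15.9% with 95% confidence resulting in a treatment strategy worthy of further investigation". Section 11.3 says that "the proportion of patients who are breast cancer free 5 years after treatment will be calculated with a 95% confidence interval". On numbers, Section 11.6 states that "the accrual goal is 50 evaluable patients (at 5 years post-treatment), target accrual is 55 patients".

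**The concern.** Aim 2 and the count rule ask the trial to rule out an IBTR of 15.9%. The second criterion asks only that an excess over 15.9% is not proven. In a study of 50 these are very different standards, because failing to show an excess is easy with so few patients. The power sentence and the failure sentence also describe an upper-tail test, while the cut-off of 3 looks like a lower-tail critical value.

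IBTR at five years is a primary objective (Section 2.1), the sample size is based on it, and this is the efficacy half of the only go/no-go rule. With 4 to 12 recurrences a report could cite Section 11.4 for either conclusion. If it followed the failure sentence it would claim a significant excess at, for example, an observed 8%.

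**Working it through.** **Inputs.** n = 50 evaluable (Sections 11.4 and 11.6); limit p0 = 5.9% + 10 points = 15.9%; assumed true rate p1 = 5.9%; alpha 0.05, sidedness not given; cut-off 3 (all Section 11.4). X is the number of recurrences, taken as binomial(50, p). Results are exact.

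**1. Which test gives a cut-off of 3?** Take H0: IBTR ≥ 15.9% against H1: IBTR < 15.9%, and find the largest c with P(X ≤ c | 0.159) ≤ 0.05.
- P(X ≤ 3 | 0.159) = 0.0002 + 0.0016 + 0.0076 + 0.0230 = 0.0324
- P(X ≤ 4 | 0.159) = 0.0835

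So c = 3 at one-sided 0.05. The plan's cut-off is reproduced, and it belongs to the test in Aim 2.

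**2. The plan's power.** P(X ≤ 3 | 0.059) = 0.0478 + 0.1499 + 0.2302 + 0.2310 = 0.6588, or 65.9%. The normal approximation gives Φ[(0.100 − 1.645 × 0.0517)/0.0333] = Φ(0.448) = 67.3%. Both are near the stated 70% without reaching it, and both are in the lower-tail direction.

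**3. The test as worded (rate above 15.9%).** Find the smallest r with P(X ≥ r | 0.159) below alpha.
- P(X ≥ 12) = 0.0895; P(X ≥ 13) = 0.0455; P(X ≥ 14) = 0.0212

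So 13 of 50 (26%) is needed at one-sided 0.05, or 14 of 50 at two-sided 0.05 (0.025 in the upper tail). Power at a true 5.9% is P(X ≥ 13 | 0.059) = 0.0000047.

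**4. The failure sentence at 4 of 50.** The observed rate is 4/50 = 8%, and P(X ≥ 4 | 0.159) = 0.968. The sentence is wrong for 4 to 12 recurrences (4 to 13 if two-sided); from 4 to 7 the observed rate (8% to 14%) is even below 15.9%. Other readings of the acceptable proportion do not rescue it: against 5.9%, P(X ≥ 4) = 0.341; against 5.9% × 1.10 = 6.49% (10% read as relative), 0.409.

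**5. Chance of passing the IBTR condition under each rule.** Literal criterion 2 passes X ≤ 12 (one-sided) or X ≤ 13 (two-sided); the count rule passes X ≤ 3.

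| True IBTR | Criterion 2, one-sided | Criterion 2, two-sided | 3 or fewer |
|---|---|---|---|
| 15.9% | 95.4% | 97.9% | 3.2% |
| 20% | 81.4% | 88.9% | 0.6% |

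**6. Sidedness.** The exact (Clopper-Pearson) one-sided 95% upper bound is 14.8% at 3/50 and 17.4% at 4/50, so it matches the count rule. The two-sided exact 95% upper limit is 16.5% at 3/50 and 13.7% at 2/50. On that reading the cut-off falls to 2 and power at 5.9% to P(X ≤ 2 | 0.059) = 42.8%.

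**7. Evaluable numbers other than 50.** With 55 accrued, and loss between none and 20% (55 × 0.80 = 44; the 20% is an assumption to show the range), the largest count whose one-sided 95% exact upper bound is below 15.9% is:

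| Evaluable | Largest passing count | Attained alpha |
|---|---|---|
| 44–46 | 2 | 0.021 to 0.016 |
| 47–54 | 3 | 0.046 to 0.020 |
| 55 | 4 | 0.0495 |

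**The case against.** The strongest reply is that the operative rule is explicit and right. Section 11.4 ends with a count of 3, Aim 2 gives the matching direction, and no cut-off of 12 or 13 appears anywhere. Because the section itself equates more than 3 with a significant excess, criterion 2 and the count rule agree on the plan's own terms. The pass rates of 95.4% and 81.4% would then describe a misreading.

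Part of this stands: n and the cut-off are sound, and the repair does not touch them. But the agreement depends on a statement that is false. Once it is corrected, criterion 2 and the count rule part company from 4 to 12 recurrences, and criterion 2 is stated just as plainly as a condition for success.

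On sidedness, it is fair that one-sided testing can be inferred from Aim 2 and the cut-off. It is also fair that the Section 11.3 interval concerns the cancer-free proportion, is not tied to the decision and has no stated method. The two-sided upper limit at 3/50 is 16.5% exact and 16.2% Wilson, but 15.2% Jeffreys and 12.6% Wald, so whether 3/50 fails depends on the method. This supports writing down which bound decides.

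Finally, cut-offs for other evaluable numbers go a little beyond rewording. They apply the same bound and are needed only if the number is not 50.

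**Conclusion.** The concern holds, and the text must be corrected before the IBTR result is interpreted. The power sentence and the failure sentence are reversed, and criterion 2 sets a far weaker standard than Aim 2 and the count rule. The two rules disagree at 4 to 12 of 50 (4 to 13 if two-sided), and at a true IBTR of 15.9% their pass rates are 95.4% and 3.2%. The gap between 65.9% and about 70% power is minor; the direction is the error.

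These figures assume a binomial count with five-year IBTR status known for all 50 patients, the 10% read as percentage points (as 15.9% in the plan confirms), and the toxicity criterion met.

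**What to change.** In Section 11.4:
- State H0: five-year IBTR ≥ 15.9% against H1: < 15.9%, one-sided alpha 0.05; reject H0 with 3 or fewer of 50 (attained alpha 0.032).
- Replace criterion 2 with: the one-sided 95% exact upper confidence bound for five-year IBTR is below 15.9%.
- Replace the failure sentence with: if 4 or more of 50 recur, an IBTR of 15.9% has not been ruled out.
- Restate power as about 66% (exact) to conclude that IBTR is below 15.9% when the true rate is 5.9%.
- Add that if the evaluable number is not 50, the cut-off comes from the same bound: 2 for 44–46, 3 for 47–54, 4 for 55.

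In Aim 2 (Section 11.1.2), say that this one-sided bound governs the decision. In Section 11.3, say that the 95% interval for the cancer-free proportion is descriptive.

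The cost is text in three sections. The sample size, the data collected and the 3-of-50 threshold do not change.

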Evaluation of Single Fraction High-gradient Partial Breast Irradiation as the Sole Method of Radiation Therapy for Low-risk Stage 0 and I Breast Carcinoma

**Washington University School of Medicine
Department of Radiation Oncology
[name]
[name]**

**Protocol#: 201401160
Version Date: 11/26/19**

Principal Investigator: **[name].**
[contact]
Email: [contact]

Sub-Investigators

[name]., Ph.D.
[name], ANP, Ph.D.
[name].
[name].
[name].
[name].

Modality

Radiation Oncology
Radiation Oncology
Radiation Oncology
Surgery
Anatomic & Molecular Pathology
Biostatistics

ClinicalTrials.gov #: NCT02076074

CONFIDENTIAL

The information contained in this document is regarded as confidential and, except to the extent necessary to obtain informed consent, may not be disclosed to another party unless law or regulations require such disclosure. Persons to whom the information is disclosed must be informed that the information is confidential and may not be further disclosed by them

**Evaluation of Single Fraction High-gradient Partial Breast Irradiation as the Sole Method
of Radiation Therapy for Low-risk Stage 0 and I Breast Carcinoma**

Protocol Revision History

[figure not shown]
Initial Approval Version	01/31/2014
Amendment #1	04/01/2014
Amendment #2	05/18/2015
Amendment #3	11/03/2015
Amendment #4	01/05/2016
Amendment #5	03/20/2017
Amendment #6	11/26/2019

Evaluation of Single Fraction High-gradient Partial Breast Irradiation as the Sole Method of Radiation Therapy for Low-risk Stage 0 and I Breast Carcinoma

SCHEMA

Study Summary

This is a phase I/II study which will evaluate the complication rates, local control, cosmetic results, and quality of life of single fraction high gradient partial breast irradiation (HG-PBI) when used as the sole method of radiation therapy for patients with pathologic stage 0 ($\leq 2 \text{ cm}$) or I carcinoma of the breast treated with partial mastectomy with histologically assessed negative surgical margins. Time to event parameters that will be collected are IBTR, mastectomy-free survival, regional recurrence rate, distant disease free survival, and overall survival.

Systemic Therapy

Cytotoxic chemotherapy, hormonal, or biologic therapies are not to be started until at least 4 weeks after radiation therapy.

Eligibility (see Section 3.0 for details)

- Ductal carcinoma in situ (*lesions $\leq 2 \text{ cm}$*)

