5.5 Duration of Follow-up

Patients will be followed according to the scheduled described in the study calendar for 5 years or until death, whichever occurs first. Patients removed from study for unacceptable adverse events will be followed until resolution or stabilization of the adverse event.

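### Does working the five-year IBTR decision only for 50 completers leave it undefined, or less powerful, when another number of patients is followed?

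*Combined protocol and SAP*

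**What the plan says.** Section 11.4 compares the five-year IBTR with 15.9%, which is 5.9% from the cited no-radiation study plus 10 points. It uses a binomial test at alpha 0.05 and states that "we will obtain approximately 70% power to detect a proportion significantly larger than 15.9" (per cent). The decision is then given as a count. Failure is introduced by "If 50 patients complete the trial and more than 3 recurrences are observed in the first five years", and the study succeeds "if 3 or fewer recurrences are observed among 50 patients and the tolerance parameters are met".

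Section 11.1.2 gives the same criterion without tying it to a sample size: "The IBTR will be less than 15.9% with 95% confidence".

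On numbers, section 11.6 says "It is estimated that less than 10% of the patients treated in this study will be lost to follow up" and "because the accrual goal is 50 evaluable patients (at 5 years post-treatment), target accrual is 55 patients to account for the 10% anticipated drop-out". Section 5.5 follows patients "for 5 years or until death, whichever occurs first". The Study Summary in the Schema lists IBTR among the time-to-event data to be collected.

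No section gives a count for any number other than 50. None says whether a recurrence seen before drop-out counts, or how a death without recurrence before year 5 enters the denominator.

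**The concern.** This is the go/no-go rule for a primary objective, and its only worked number is conditional on 50 completers. With 55 accrued and each patient having a 10% chance of loss, exactly 50 are followed in only 18% of trials; at 5% loss the figure is 8%. Read as a fixed pass mark, a count of 3 becomes stricter as more patients are followed and laxer as more are lost. Better follow-up would then make a treatment with the expected IBTR less likely to pass, while heavy loss could push the type I error above 5%. The analyst would also be choosing the cut, the numerator and the denominator after the data are in. A cumulative incidence estimate with an upper confidence bound would avoid dependence on the number of completers, and the data for it are already collected.

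**Working it through.** **Inputs.** Unacceptable rate p0 = 0.159 (11.1.2, 11.4); expected rate p1 = 0.059 (11.4); alpha 0.05 (11.4); 55 accrued, under 10% lost, 50 evaluable (11.6). 55 × 0.9 = 49.5, so the plan expects about 50 to 55 followed.

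**The plan's own cut.** With X ~ Binomial(n, p) and success if X ≤ c, alpha is P(X ≤ c | p0) and power is P(X ≤ c | p1). At n = 50:

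- c = 3: alpha = 0.0002 + 0.0016 + 0.0076 + 0.0230 = 3.24%; power = 0.0478 + 0.1499 + 0.2302 + 0.2310 = 65.9%.
- c = 4: alpha = 8.35%, too high.

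So 3 of 50 is the largest count with exact one-sided alpha at or below 5%. This shows which test the count came from. (The 65.9% falls short of the stated 70% at n = 50 itself, so that gap has nothing to do with follow-up and is a separate matter.)

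**The same test at other numbers followed.**

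| n | alpha / power, cut kept at 3 | largest cut with alpha ≤ 5% | alpha / power at that cut |
|---|---|---|---|
| 46 | 5.18% / 71.3% | 2 | 1.62% / 48.5% |
| 47 | 4.62% / 70.0% | 3 | same |
| 50 | 3.24% / 65.9% | 3 | same |
| 52 | 2.55% / 63.2% | 3 | same |
| 54 | 2.00% / 60.4% | 3 | same |
| 55 | 1.77% / 59.1% | 4 | 4.95% / 77.7% |

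From 51 to 54 a cut of 4 would break alpha (5.51% at n = 54), so 3 is the right cut and the drift in power is the discreteness of an exact test. With complete data the log-log upper bound makes the same decisions: 3/50 gives 14.8% (pass), 4/50 gives 17.3% (fail), 4/54 gives 16.1% (fail), 4/55 gives 15.8% (pass). Only n = 55 differs from a carried-over 3. That needs no loss at all, with probability 0.90^55 = 0.3% at 10% loss and 0.95^55 = 6% at 5% loss.

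**Averaged over the number followed.** Take n ~ Binomial(55, 1 − loss), independent of recurrence. The first two rows count completers only and average the binomial results over n. The third is a simulation of 55 treated patients with exponential recurrence and loss and no deaths.

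| Rule | 5% loss, alpha / power | 10% loss, alpha / power |
|---|---|---|
| Cut kept at 3 | 2.5% / 62.8% | 3.6% / 66.6% |
| Plan's test at the realised n | 2.7% / 63.9% | 3.2% / 64.5% |
| One-sided 95% cumulative incidence bound | 2.7% / 64.4% | 2.7% / 63.5% |

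**Counting conventions.** Keeping the cut at 3 but counting every recurrence seen, including those before drop-out, gives a simulated alpha of 2.1% at 5% loss and 2.6% at 10% loss, against 2.6% and 3.6% in the same simulation for completers only. All are below 5%. For deaths the documents give no rate. Removing a patient who died without recurrence lowers the denominator by one, and the cut does not move anywhere between 47 and 54.

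**The case for a change.** The strongest reply is that the general criterion does not settle the rule. Sidedness is not stated, and a two-sided 95% interval leaves 2.5% in the tail. On that reading 3 of 50 (3.24%) would fail and the cut would be 2. Read literally, a rate that merely must not be significantly above 15.9% would pass up to 12 of 50, since P(X ≥ 13 | 15.9%) = 4.6%. The claim that more than 3 of 50 is significantly larger than the acceptable proportion is also reversed, because 4/50 = 8%. On this view only the count is usable, and it exists at one sample size. With 4 recurrences in 55 a carried-over count says stop while the stated alpha says go.

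The wording is indeed loose. But those ambiguities are present at n = 50 too, and the stated count resolves them there: of these readings, only the one-sided 5% test against 15.9% yields 3 of 50. An analyst who has identified the test can apply it at another n without a new choice.

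It is also true that heavy loss would hurt. With 46 or fewer followed (9 or more of 55 lost), a carried-over 3 counted in completers only exceeds 5%: 5.2% at n = 46, and on average 4.9% at 15% loss and 6.8% at 20%. At 10% loss, 46 or fewer occurs in 9% of trials, yet the average stays at 3.6%. The inflation needs three things together: a cut the plan does not carry over, a completers-only count it does not state, and loss beyond what it expects. Section 11.4 speaks of recurrences observed in the first five years, which fits counting every one seen; alpha is then 2.9% at 15% loss and 3.6% at 20%.

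**Conclusion.** The concern does not call for a change. The fall from 65.9% to 59.1% arises only if the count for 50 completers is imposed on 55, which the plan does not say. For 51 to 54 followed, the correct cut is 3 in any case, so neither a table of cuts nor, with complete data, a cumulative incidence bound would restore the power. At 55 the plan's own alpha already gives a cut of 4.

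What remains is unwritten detail: the cut at other numbers, recurrences before drop-out, and deaths. Within the planned 50 to 55, alpha with a cut of 3 is 1.8% to 3.2%. Replacing the count by a bound moves power by about one point at 5% or 10% loss and would swap an exact test for a large-sample approximation resting on about three events (50 × 0.059 = 2.95), a choice statisticians could reasonably dispute. The bound is clearly better only from about 15% loss (64% power against 60% for the plan's test at the realised n). The stakes are also limited, since success leads only to further study.

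This rests on the one-sided 5% reading that reproduces 3 of 50, loss independent of recurrence and under about 10%, and few deaths within five years, for which the documents give no figure.
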